##### **Cohort 2:**

Cohort 2 is now formally closed. This cohort had sought to enrol patients who are chemo-naïve (first-line setting) for CUP, with a PS 0-2.

\*\*\*\*\*

Patients will undergo screening procedures during a standard 28-days time window from initiation of the study, under standard GCP and informed consent. Restaging will be performed by computerized tomography using ir-RECIST criteria at 3 months from initiation of systemic treatment and on an 8 weekly basis thereafter until radiological proven disease progression or intolerance or patient choice.

The EORTC QLQ-C30 questionnaire (to assess the quality of life) will be done at baseline after 3 months and then at discontinuation of study treatment.

Correlative translational study samples (blood) and tissue (used for histological confirmation and to document PD-L1 expression) will be collected at baseline, and blood and serum samples monthly (after an informed optional consent and banked for retrospective immune-modulating and other biomarkers for future research and analysis). Patients will also be separately consented to the NHSE CUP 100K genome project that will be running in the UK by 2018, for deep sequencing of tumor tissue and germ-line, in centers participating in, or with access to the UK framework for this programme.

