#### **5.9.15 Tumour Assessments**

Tumour assessments will be performed using CT contrast or MRI scans of the chest, abdomen and pelvis at the time-points indicated in Table 3. The same method used for assessment at baseline must be used at all subsequent time points.

Tumour assessment will include: if disease is measurable or non-measurable (at least one lesion must be measurable), date of assessment, imaging method used, site (breast, lung, liver, pleural effusion, local lymph nodes, distant lymph nodes, bone, brain or other site), longest diameter of each target lesion and sum of longest diameters for all target lesions.

Patient response to treatment will be assessed using RECIST v1.1. Tumour size, progression free survival and objective response rate will all be determined. The RECIST v1.1 (January 2009) guidelines for measurable, non-measurable, target and non-target lesions and the objective tumour response criteria (complete response, partial response, stable disease or progression of disease) are detailed in Appendix A.

Tumour size will be assessed at baseline and on scans at subsequent time points and recorded as the sum of the longest diameters of the target lesions. Baseline assessment should be performed no more than 28 days before the start of study treatment and ideally as close as possible to the start of study treatment; it should include all areas known for possible breast cancer metastases. Subsequent tumour assessments will be conducted every 12 weeks from C1D1, the window for each assessment is  $\pm 7$  days. During the period of the COVID-19 pandemic, this window period can be increased from -1 to a 2 week interval.

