### 8.2 Sample size, power considerations and planned recruitment rate

An interim futility analysis was originally pre-planned after recruiting 24 (out of 57) patients in Cohort 2 and a final analysis after 77 participants completed the study (20 for Cohort 1 and 57 for Cohort 2).  $\geq 1$  documented response in Cohort 1 was achieved in May 2020, enabling Cohort 2 to open and Cohort 1 to close once sufficient evaluable participants had been enrolled. Due to the unexpected challenges recruiting study participants outlined in the Trial Summary and sections 1.3.1 and 3.1, particularly for Cohort 2, Cohort 1 was reopened and expanded. Version 7.0 of the protocol has formally closed Cohort 2 with approval from the TMG, MSD and combined TSC/IDMC. Cohort 1 (pre-treated patients) remains a crucial area of unmet need with no standard of care treatment existing.

The study statistics were originally modelled on the UK CUP-ONE trial based on the primary study end-point of response in cohort 2.

The sample size has thus been recalculated to accommodate the shift of focus to assessing PFS and OS in Cohort 1 and complete removal of Cohort 2. The sample sizes were recalculated based on the Brookmeyer-Crowley test for median survival time (Brookmeyer R and Crowley JJ. A confidence interval for the median survival time. Biometrics. 1982: 38, 29-41).

CUPem	C/37/2017	Imperial College London	V7.0, 08.12.2021
-------	-----------	----------------------------	------------------

Assuming a historic null PFS of 2 months and an alternative PFS of 4 months, the minimum required sample size to determine the median PFS for the study cohort is 46 (at 0.05 level of significance, one-sided, 90% power). For the OS, assuming a null OS of 4 months and an alternative OS of 7 months, the required minimum sample size is 67 with the same level of significance and power. Therefore, the final sample size needed to determine both the median PFS and OS is 67 (the higher sample size). In the event that this sample size will be difficult to recruit within the additional accrual period of 12 months, a sample size of 31 will still be able determine the median PFS and 45 the median OS with a power of 80%.

Power Size	Null Median Survival	Alternative Median Survival	Min Sample Size
0.80	2 months PFS	4 months	31
0.90	2 months	4 months	46
0.80	4 months OS	6 months	83
0.80	4 months	7 months	45
0.90	4 months	6 months	122
0.90	4 months	7 months	67

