### 8.3 Patient Replacement Strategy

Patients assessable for the primary end-point for both cohorts of the study are those that have received at least 2 cycles of Pembrolizumab and are assessable for toxicity. If there is documented clinical or radiological progression, prior to the first planned radiological CT assessment at 12 weeks then the subject(s) are classified as treatment failures. Enrollment of additional subjects to fulfill the study targets can only be considered in those that have **not** progressed but have not completed the minimum of 2 cycles for whatever reason. This will be discussed on a case by case basis, by the lead investigators in participating sites via the chief investigator and the TMG.

CUPem	C/37/2017	Imperial College London	V7.0, 08.12.2021
-------	-----------	----------------------------	------------------

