3.5 Sample Size

1) In the first cohort 20 second-line (or more) patients will be accrued; if no responses or benefit is observed in 20 assessable patients, accrual of the whole trial will stop at this point. “Assessable” is defined as patients who have had at least 2 cycles of Pembrolizumab and are assessable for response at a minimum of 6 weeks post-study start.

2) The study statistics were originally modelled on the UK CUP-ONE trial based on the primary study endpoint of response in cohort 2.

An interim futility analysis was originally pre-planned after recruiting 24 (out of 57) patients in Cohort 2 and a final analysis after 77 participants completed the study (20 for Cohort 1 and 57 for Cohort 2). ≥1 documented response in Cohort 1 was achieved in May 2020, enabling Cohort 2 to open and Cohort 1 to close once sufficient evaluable participants had been enrolled. Due to the unexpected challenges recruiting study participants outlined in the Trial Summary and sections 1.3.1 and 3.1, particularly for Cohort 2, Cohort 1 was reopened and expanded and the initial version 7.0 of the protocol has formally closed Cohort 2 with approval from the TMG, MSD and combined

TSC/IDMC. Cohort 1 (pre-treated patients) remains a crucial area of unmet need with no standard of care treatment existing.

The sample size has thus been recalculated to accommodate the shift of focus to assessing PFS and OS in Cohort 1 and complete removal of Cohort 2. The sample sizes were recalculated based on the Brookmeyer-Crowley test for median survival time (Brookmeyer R and Crowley JJ. A confidence interval for the median survival time. Biometrics. 1982: 38, 29-41).

Assuming a historic null PFS of 2 months and an alternative PFS of 4 months, the minimum required sample size to determine the median PFS for the study cohort is 46 (at 0.05 level of significance, one-sided, 90% power). For the OS, assuming a null OS of 4 months and an alternative OS of 7 months, the required minimum sample size is 67 with the same level of significance and power. Therefore, the final sample size needed to determine both the median PFS and OS is 67 (the higher sample size). In the event that this sample size will be difficult to recruit within the additional accrual period of 12 months, a sample size of 31 will still be able determine the median PFS and 45 the median OS with a power of 80%.

Power	Null Median Survival	Alternative Median Survival	Min N
0.80	2 months PFS	4 months	31
0.90	2 months	4 months	46

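### PFS is sized on a test at 2 months, but no on-treatment scan is scheduled before about week 12, so the 5% error rate depends on how many early progressions are noticed without a scheduled scan

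*Protocol*

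**What the plan says.** On the test, Protocol 8.2 states: "The sample sizes were recalculated based on the Brookmeyer-Crowley test for median survival time". It continues: "Assuming a historic null PFS of 2 months and an alternative PFS of 4 months, the minimum required sample size to determine the median PFS" is 46, at a one-sided 0.05 level with 90% power. For slow recruitment it says that "a sample size of 31 will still be able determine the median PFS and 45 the median OS with a power of 80" per cent. SAP 3.5 repeats the premise: "Assuming a historic null PFS of 2 months and an alternative PFS of 4 months". The null for overall survival (OS) in the same paragraph is 4 months.

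On imaging, Protocol 5.9.15 says: "Subsequent tumour assessments will be conducted every 12 weeks from C1D1", with a window of 7 days either side that may be widened to two weeks during the pandemic. Protocol 3.1 puts restaging "at 3 months from initiation of systemic treatment and on an 8 weekly basis thereafter until radiological proven disease progression". Table 3 shows the first on-treatment scan at cycle 5. A scan at discontinuation is needed only if none was taken in the preceding 12 weeks.

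Protocol 8.3 classes a patient as a treatment failure on documented clinical or radiological progression "prior to the first planned radiological CT assessment at 12 weeks".

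SAP 5.1 dates PFS from enrolment to first evidence of progression, or death, and promises a median with a 95% confidence interval. It has no rule for progression that occurs between scans. SAP 6.3 calls the PFS summary descriptive, while the opening of SAP 6 sets two-tailed 5% testing for primary and secondary outcomes.

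**The concern.** A Brookmeyer-Crowley test of a 2-month median asks whether the Kaplan-Meier estimate at 2 months is above one half. Only events dated by day 61 enter it, and no scheduled on-treatment scan has taken place by then. A patient whose tumour grew in the first month, but who was clinically stable and had no unscheduled imaging, is still counted as progression-free at month 2.

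The discontinuation scan does not close this gap. A baseline scan may be up to 28 days old at the start of treatment, so it satisfies the 12-week rule for any stop up to at least day 56 (84 − 28), and for later stops if baseline imaging was nearer to day 1.

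At stake is whether an inactive drug could appear to exceed historic PFS because of the scan calendar, in a single-arm trial with no control group to reveal it. PFS is also one of the two supports for the 31-patient minimum.

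**Working it through.** **Inputs.** PFS 2 v 4 months, OS null 4 months, one-sided 5%, n = 31, 46 and 67 (Protocol 8.2, SAP 3.5). First scan on day 84 ± 7 (Protocol 5.9.15). Assumptions: exponential times and no censoring before month 2. The share c of non-fatal progressions noticed in time without a scheduled scan is not in the documents, so it is varied.

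**1. Reproduce the plan's figure.** Under the alternative, S(2) = 0.5^(2/4) = 0.707; under the null it is 0.5. Then n = [(1.645 × 0.5 + 1.282 × √(0.707 × 0.293)) / 0.207]² = 46.1, against the stated 46. At 80% power this formula gives 33.9; with the alternative variance only it gives 29.9. The stated 31 lies between. So the sizing is a test of S(2) = 0.5.

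**2. Dates.** Two months is day 61. Day 84 is 84/30.44 = 2.76 months, day 77 is 2.53, and day 70 is 2.30. All fall after month 2.

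**3. Observed survival at month 2 when the null is true.** Half the patients have progressed or died. With median OS 4 months, 1 − 0.5^(2/4) = 29.3% have died, so 20.7% have a non-fatal progression. Observed S(2) = 0.5 + (1 − c) × 0.207. If c = 0 this is 0.707, the same as under the 4-month alternative, so the false-positive rate equals the power.

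**4. One-sided false-positive rate.** Binomial tails at the observed S(2). Exact cut-offs are 21/31, 30/46 and 41/67. The Brookmeyer-Crowley rule with Greenwood standard error gives 20/31, 29/46 and 41/67.

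| c | S(2) | n=31 exact / Greenwood | n=46 exact / Greenwood | n=67 (both) |
|---|---|---|---|---|
| 1 | 0.500 | 3.5 / 7.5% | 2.7 / 5.2% | 4.3% |
| 0.75 | 0.552 | 10.9 / 19.4% | 11.0 / 17.8% | 19.3% |
| 0.5 | 0.604 | 25.8 / 39.1% | 30.3 / 41.6% | 49.7% |
| 0 | 0.707 | 71.9 / 83.1% | 83.7 / 90.2% | 96.5% |

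The normal approximation at n = 46 gives 5, 17, 40 and 90%. Apart from small steps due to discreteness, the rate rises with n when c < 1, because this is bias and not noise. At a two-sided 5% level, the exact rates at n = 46 are 1, 6, 21 and 75%.

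**5. Where the median lands.** Just before day 84, true PFS is 0.5^(2.76/2) = 0.384 and OS is 0.5^(2.76/4) = 0.620. Observed survival is 0.384 + (1 − c) × 0.236, which stays above 0.5 when c is below about 0.51. A true 2-month median then reads as about 2.76 months. At c = 0.75 it reads as 2.34.

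**The case against.** Four objections have force.

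- **PFS may not be tested at all.** The Brookmeyer-Crowley test appears only in the sample-size text. SAP 6.3 is descriptive, and the Protocol summary calls the trial hypothesis-generating. This stands: it cannot be said that the plan will certainly run this test. But SAP 6 says that primary outcomes will be tested, PFS is listed under the primary endpoint, and a median with a confidence interval set against 2 months carries the same bias.
- **Early events can be caught.** Patients attend every three weeks for performance status, tumour markers and, as indicated, examination, and Protocol 8.3 recognises progression before week 12. A reader might infer that no scan can enter the test; the documents support only that no scheduled scan does. A reader might also take 90% as the expected error rate. That needs every non-fatal progression to go unnoticed for two months, which Protocol 8.3 does not suggest.
- **The historic 2 months may have been measured on a similar schedule.** If so, the inflation shrinks or disappears. The documents give neither its source nor its scan interval, so this can be neither relied on nor excluded.
- **The SAP already has a 12-week binomial test.** Its disease control rate (DCR) test (20% v 40%, at least 10 of 31) also supports the minimum of 31. It does not repair the PFS comparison, and any new landmark must be reconciled with it.

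It is also tempting to add the conflicting later scan intervals to this point. They concern scans after the first and cannot affect the estimate at 2 months. The six-week assessability wording in SAP 3.5 does not help the plan either, because no six-week scan is scheduled.

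**Conclusion.** The point holds in conditional form. The sizing test looks at month 2, before any scheduled on-treatment scan. Its stated 5% is met only if essentially all early progressions are noticed by other means, or if the historic 2 months was measured comparably.

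Missing a quarter of the non-fatal progressions takes the one-sided error at 46 patients to 11–18%; missing half takes it to 30–42%. These figures rest on exponential times, both planning nulls being true and no early censoring. The noticed share is unknown, so no single value is established. That the drug would in fact pass falsely, or that the reported median must be 2.76 months, does not follow from the documents.

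**What to change.** In Protocol 8.2 and SAP 3.5, 5.1 and 6.3:

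- Do not judge median PFS, or its 95% interval, against 2 months. Report it descriptively, with an interval-censored estimate.
- Base any PFS comparison on the proportion alive and progression-free at 13 weeks (day 91 = 2.99 months), when the standard first-scan window has closed. Count progression found at the first scan as failure whatever its date. If exponential, the null is 0.5^(2.99/2) = 35.5% and the alternative 0.5^(2.99/4) = 59.6%. Exact binomial examples: 16/31 (alpha 4.8%, power 86%), 23/46 (3.0%, 93%), 31/67 (4.5%, 99%).
- State how unassessed patients are counted and include them in the power. As an illustration, if 10% are unassessed and count as failures, the alternative becomes 0.9 × 59.6% = 53.6% and power falls to about 66, 74 and 91%.
- Check the cut-offs over the scan window. If every scan fell on day 84 and nothing was noticed between then and day 91, the null rate could reach 38.4% and alpha 9.4, 7.3 and 11.7%. On day 77 it could reach 41.6%, with alpha about 17, 16 and 26%. The landmark reduces the dependence on the calendar but does not remove it.
- Reconcile the landmark with the DCR test. A DCR of 40% at day 84 corresponds to a median of 2.76 × ln 0.5 / ln 0.4 = 2.1 months, so the desired DCR sits close to the PFS null.
- Align the one-sided 5% in the sizing text with the two-tailed 5% in SAP 6.
- Give the source and scan interval of the historic 2 months.

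The cost is wording and a short recalculation, with no extra scans or patients. The downside is that the converted rates depend on the survival shape: for Weibull shape 0.8 to 2, the 13-week null 0.5^((2.99/2)^shape) runs from 38% to 21%.

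As a separate consistency point, the later scan interval is 8-weekly in Protocol 3.1 and SAP 3.1; 12-weekly in Protocol 5.9.15, Table 3 footnote g and SAP 6.1; and cycle 5 then cycle 8 in Table 3. These passages must be reconciled, since the interval shifts the observed median PFS.

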The study will therefore aim to recruit between 31 and 67 patients to Cohort 1 within the allotted study period. This sample size range is estimated to have a power of 80% to 90% in determining the PFS and/or the OS of the study cohort.

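### The 80% to 90% power stated for 31 to 67 patients does not hold for OS, or for PFS and OS together, if the trial ends with 31 to 44 patients

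*Protocol*

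**What the plan says.** Protocol 8.2 and SAP 3.5 carry the same calculation. On the method: "The sample sizes were recalculated based on the Brookmeyer-Crowley test for median survival time". On the error rates of the main design: "at 0.05 level of significance, one-sided, 90% power".

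The PFS hypothesis is introduced with "Assuming a historic null PFS of 2 months and an alternative PFS of 4 months". Its sample size is then put this way: "the minimum required sample size to determine the median PFS for the study cohort is 46". The OS calculation is described as "assuming a null OS of 4 months and an alternative OS of 7 months". The number that results from it is reported in these words: "the required minimum sample size is 67 with the same level of significance and power". The larger figure, 67, is taken as the number needed for both endpoints. As a fallback if accrual is slow, "a sample size of 31 will still be able determine the median PFS and 45 the median OS with a power of 80"%.

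The table prints 31, 45 and 83 patients for 80% power (PFS 2 v 4; OS 4 v 7; OS 4 v 6 months) and 46, 67 and 122 for 90%.

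The closing sentence then covers the whole range of 31 to 67: "This sample size range is estimated to have a power of 80% to 90% in determining the PFS and/or the OS".

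The Protocol's Trial Summary and section 1.3.1 close recruitment at 67 patients or at the end of December 2022, whichever happens first. SAP Section 1 gives the same end date.

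**The concern.** The closing sentence merges two endpoints that need different numbers. The lower end of the range, 31, comes from the PFS row at 80%. The upper end, 67, comes from the OS row at 90%. No single endpoint has 80% power at one end and 90% at the other.

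OS is listed under the primary objectives (Protocol 2.1, SAP 2.1), and the sample size was recalculated for PFS and OS in Cohort 1. The plan itself describes recruitment as difficult, so a final number in the thirties or low forties is foreseen. If the trial ends there and the OS result is not significant, a reader relying on the sentence would take it as a negative finding from a test with at least 80% power. The actual chance of missing a true 7-month median would be about a third or more.

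**Working it through.** **Check from the documents alone.** The table needs 45 patients for 80% OS power at 4 v 7 months. Power rises with sample size, so 31 to 44 patients give less than 80% for OS. Power to succeed on both PFS and OS cannot exceed the power for OS, so it is also below 80%.

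**Size of the shortfall.** The plan states no survival distribution, scale, variance or censoring, so I assume exponential survival and no censoring before the null median m0. The test is then of S(m0) = 0.5 against p = 0.5^(m0/m1), one-sided 5% (z = 1.645).

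- PFS 2 v 4: p = 0.5^(2/4) = 0.707, difference d = 0.207, s = √(p(1−p)) = 0.455.
- OS 4 v 7: p = 0.5^(4/7) = 0.673, d = 0.173, s = 0.469.
- OS 4 v 6: p = 0.5^(4/6) = 0.630, d = 0.130, s = 0.483.

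Formula A (null variance for alpha, alternative variance for power): n = [(1.645 × 0.5 + z_β × s)/d]².

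Formula B (alternative variance throughout): n = [(1.645 + z_β) × s/d]².

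The plan's own figures first:

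| Row | Printed n | A: n | A: power at printed n | B: n | B: power at printed n |
|---|---|---|---|---|---|
| PFS 2 v 4, 80% | 31 | 33.9 | 76.6% | 29.9 | 81.3% |
| OS 4 v 7, 80% | 45 | 49.5 | 76.4% | 45.5 | 79.6% |
| OS 4 v 6, 80% | 83 | 89.4 | 77.3% | 85.3 | 79.0% |
| PFS 2 v 4, 90% | 46 | 46.1 | 90.0% | 41.3 | 92.5% |
| OS 4 v 7, 90% | 67 | 67.8 | 89.7% | 63.0 | 91.5% |
| OS 4 v 6, 90% | 122 | 123.0 | 89.8% | 118.2 | 90.8% |

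Formula A is close on the 90% rows and Formula B on the 80% rows. On the log-log scale (null variance for alpha, alternative for power), all six rows come within 2 points of their stated power: 78.8%, 78.4% and 78.7% for the 80% rows; 89.5%, 89.5% and 89.8% for the 90% rows. No single variant matched all six sample sizes, but the table as a whole is plausible.

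OS power (4 v 7) at n = 31, with √31 = 5.568:

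- A: Φ[(0.173 × 5.568 − 0.822)/0.469] = Φ(0.30) = 61.8%.
- B: Φ[0.173 × 5.568/0.469 − 1.645] = Φ(0.41) = 65.8%.
- Log-log: 66.3%.
- Exact binomial (reject at 21 or more of 31 alive at 4 months; size 3.5%): 56.4%.
- Wald test with estimated variance: 70.4%, with true size 7.5%, so it is not a 5% test.

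Every version falls short of 80%.

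PFS power (2 v 4) at n = 31: 76.6% (A), 78.8% (log-log), 81.3% (B), 71.9% (exact), 83.1% (Wald, same inflated size). The printed 80% lies within this range.

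**Effect of a two-tailed test.** SAP Section 6 tests at two-tailed 5%. With z = 1.960 in Formula A, power at 31 is about 65% for PFS and 49% for OS, and OS power at 67 is about 82%.

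**The case against.** The sentence says PFS and/or OS. Read as PFS alone, it is acceptable at 31, and the preceding paragraph separates 31 for PFS, 45 for OS and 67 for both. A careful reader can therefore find the OS limit. That stands, and it is why the sentence cannot be called false without qualification. It does not rescue the OS reading or the joint reading, and both are natural given that the recalculation was for PFS and OS.

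A reader might go further and infer that the 80% rows are miscalculated and should be 34, 50 and 90. The documents do not support that. Those numbers follow from Formula A only, and the plan names no variance or scale; Formula B gives 29.9, 45.5 and 85.3 against the printed 31, 45 and 83. Nor does Formula A strictly reproduce the 90% rows: 46.06, 67.76 and 122.97 round up to 47, 68 and 123, so the match needs rounding down. For the same reason, a claim that PFS power at 31 is 77% instead of 80% fails.

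It is also fair to say that SAP 6.3 only summarises OS and PFS by medians and Kaplan-Meier curves, and that the trial is labelled hypothesis generating. No specific OS test or decision rule is set out, so the risk lies in how a result would be interpreted against the stated power. That moderates the consequence but does not make the power statement correct. Finally, lower power against a 6-month OS median is not hidden: the table prints 83 and 122 for it.

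**Conclusion.** The point holds in a limited form. By the plan's own table, the 80% to 90% statement is wrong for OS, and for PFS and OS jointly, at final numbers of 31 to 44. At 31 the OS shortfall is about 14 to 18 percentage points by the large-sample formulas (80 − 66 to 80 − 62), about 24 by the exact test, and about 10 for the Wald test with inflated size. The contradiction itself needs no assumptions. Its size rests on exponential survival, no censoring before 4 months and a one-sided 5% level. The PFS figure at 31 and the printed 80% rows are not shown to be in error.

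**What to change.** In Protocol 8.2 and SAP 3.5, replace the pooled sentence with power by endpoint and sample size: at 31, PFS about 80% and OS about 62% to 66%; at 45, OS about 80%; at 67, OS about 90%. Beside these figures, state the survival distribution, scale, variance and censoring assumptions and the one-sided 5% level. Confirm the figures under whichever method was actually used.

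Add that with fewer than 45 patients OS has less than 80% power, so a non-significant OS result there is not evidence of no effect.

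Leave the 80% rows at 31, 45 and 83 unless the stated method gives something else.

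Reconcile the two-tailed 5% test in SAP Section 6 with the one-sided design, and say whether any test of median OS or PFS will be done, since SAP 6.3 describes none. If the two-tailed test is kept, the powers above must be lowered.

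The cost is a text amendment to two documents, with no extra patients, visits or data.
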